PROTOCOL of the study

Versie 1 – 21 december 2023

Integrated genetic and functional analysis of the influence of menstrual products on intimate female health (abbreviated as 'Luna' project).

Research study at Antwerp University Hospital and the University of Antwerp, in a collaboration between Faculty of Medicine and Health Sciences and Faculty of Science, Department of Bioengineering

Inclusion/exclusion criteria

Volunteers
Age: 18+
Gender: F
Not pregnant
Not menopausal
Natural menstrual cycle, copper IUD or combination pill
Regular menstrual cycle
No reproductive disease (endometriosis, PCOS,..)
No history of Toxic Shock Syndrome (TSS), sensitivity or allergy to menstrual hygiene products

Furthermore, selections will be made based on the questionnaire in order to achieve a balanced study population.

Recruitment of participants

The volunteers (n=500) will be recruited through the channels built up in the Isala project (EDGE000471), such as the website (www.isala.be), instagram (Isala_UAntwerp), twitter (Isala_UAntwerp) and Linkedin (Isala). Thus, a large community has already been built, consisting of women who are very eager to participate in follow-up research. These channels will be used to obtain a representative group. Staff and students of the UAntwerpen and the UZA will also be recruited through posters, ad valvas and mails. No students will be recruited who have yet to take exams from the relevant members of the study. The volunteers will receive the information about the study and a consent form during information sessions, during which the self-sampling kit and menstrual products can also be distributed.

[figure not shown]
Sample collection

Samples will be self-sampled by the selected volunteers (n = 100). The self-sampling kit contains a detailed manual, information brochure and all materials needed by the volunteers for sample collection, storage and delivery to [name] lab. Participants will have 3 sample collections for each menstrual product. This will consist of a vaginal, vulvar and groin swab, and during menstruation the menstrual blood will also be collected, this in the case of the cup directly and in the case of the other products as the product itself, this via non-transparent sterile sealed bags provided for this purpose. These products are a tampon, a sanitary pad, a menstrual cup and 2 types of menstrual underwear, 1 with a cotton lining and 1 with a bamboo lining.

TIMELINE LUNA

[figure not shown]
Participants

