- n = 100 for 5 menstrual cycles use each cycle another menstrual hygiene product
- n = 50 combination pill, n = 50 natural cycle (no hormonal contraception)
 - Regular (predicable) menstrual cycle
 - No reproductive condition that could affect the menstrual cycle (Endometriosis, endometritis, PCOS)
 - No vaginal irritations in the last 3months
 - No pregnancy desire in the next 5 months
 - No allergies/sensitivity, no history of TSS
 - No antibiotics/antimycotics/probiotics in the last 3 months
 - No probiotics and vaginal douching during the study

Sample type

- Menstrual blood/tampon/pad/underwear
Groin skin swab
Vulvar swab
Vaginal swab

[figure not shown]

Collection procedure

- Menstrual blood collection
- Tampon/Menstrual pad/Menstruation underwear collection

Techniques

- Microbial profiling (Shotgun sequencing)
 - All samples
- Untargeted metabolomics
 - Vaginal swab
 - Menstrual blood (via cup)
- Immunological assay (ELISA)
 - Vaginal swab
 - Menstrual blood (via cup)

Sample size calculation

Power analyses are challenging for microbiome studies because the magnitude and variance of effects on the microbiome are unknown and are highly individual-dependent and different for each bacterium. However, from literature review and our experience with the Isala study, we assume that the sample size selected is reasonable. Thus, initially recruited participants (n=1500) will complete a

comprehensive questionnaire regarding their health, lifestyle, menstrual hygiene and vaginal hygiene. Based on this questionnaire, a selection will be made ($n = 100$) of participants who will participate in the actual intervention study, in order to obtain a balanced study population, as well as based on location to make the study logistically feasible.

Thus, with 50 participants per condition (half natural cycle, half combined pill) in time series, we can perform paired analyses that allow us to account for intra-personal variation and increase power. Due to the nature of the study, no wash-out period will be necessary during the different interventions, as this is already natural between 2 menstruations, this also makes each participant a separate control and does not require varying the order of menstrual products. From our own experience with longitudinal studies, we take into account 5-10% dropout. If it is larger, we will recruit additional participants to avoid undermining the study.

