We examine the influence of menstrual products at different levels. A PERMANOVA test will allow us to examine the overall effect of the intervention on the composition of the microbiome. Furthermore, we will investigate the effect on alpha diversity, for which health associations are known in the vaginal microbiome. This can be examined with a mixed effect model. Differential abundance of individual taxa will also be tested. It has been found that test tools for differential abundance often do not agree in reported results. To compensate for this, we have developed a consensus-based way in which several differential abundance testing tools are used and a taxon/condition is considered significant only if multiple tools agree. Three tools are capable of including random effects for paired analysis. Finally, for the vaginal microbiome, we test the effect on taxa modules known to be associated with lifestyle factors. This multi-level approach gives us a broad view to detect effects that may not be visible at a single individual level.

Analysis of samples

Laboratory of Applied Microbiology and Biotechnology [name], Faculty of Science, Department of Bioengineering, UAntwerpen

Part 1: Microbiome Analysis

Microbial DNA and RNA will be isolated from swabs and menstrual blood (collected via menstrual cups and extracted from the other menstrual products) via a commercial extraction kit such as the Qiagen PowerFecal DNA kit and the Qiagen RNeasy kits (cfr. Human Microbiome Project). The isolated DNA and RNA (converted to cDNA) will then be analyzed via shotgun sequencing and (meta)transcriptomics. Shotgun sequencing

and (meta)transcriptomics allow to study the functional profiles and composition of these microbial communities. Combined, these techniques will provide valuable insights into better understanding the role of microbial communities in the context of health and the influence by menstrual products. The Illumina sequencing platform will be used.

Milestone: Identification of the (functional) microbiome composition of swabs and menstrual blood, with the aim of mapping the influence of menstrual products

Part 2: Quantitative analysis of concentration of specific microorganisms

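### Does the differential-abundance consensus let tools that ignore pairing decide which taxa are reported?

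*Protocol*

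**What the plan says.** The Sample size calculation section gives no formal power figure. It supports the number of women partly by the repeated-measures design: "we can perform paired analyses that allow us to account for intra-personal variation and increase power". Two points in the same part of the protocol matter here.

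- **The decision rule and the tools.** Several tools are run on single taxa, and "a taxon/condition is considered significant only if multiple tools agree. Three tools are capable of including random effects for paired analysis". The reason given for the rule is that such tools often disagree.
- **What is left open.** No tool is named, and neither the total nor the agreement threshold is given.

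The data structure comes from the Participants list and the Sample collection section: "n = 100 for 5 menstrual cycles use each cycle another menstrual hygiene product", half of the women on the combination pill and half with a natural cycle, and "Participants will have 3 sample collections for each menstrual product". Product is therefore a within-woman contrast and contraceptive group a between-woman contrast. Alpha diversity is assigned to a mixed-effects model.

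**The concern.** Saying that three tools can carry a random effect suggests that others in the set cannot, and nothing expressly keeps those others out of the vote. A method that ignores the participant errs in opposite directions in the two contrasts.

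- **Product effects.** Ignoring the pairing leaves between-woman variation in the error term. If such a tool must agree, the consensus can be no more powerful than that tool, and the benefit of pairing is lost.
- **Pill versus natural cycle.** Treating up to 3 × 5 = 15 samples per woman (per body site) as independent understates the standard error. Two tools making the same mistake would tend to be wrong together, so their agreement protects little.

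The consensus decides which taxa are reported, so a faulty rule would affect the main taxon-level output.

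**Working it through.** The protocol states no alpha, power, effect size, variance or correlation, so there is no figure of its own to reproduce. The following is an illustration.

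**Inputs from the protocol:** 100 women; 5 products; 3 collections per product; 50 versus 50 by contraception; three tools able to include random effects.

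**Assumed inputs:** two-sided alpha 0.05; within-woman correlation ρ of 0.3 to 0.7; outcome on a normal scale with SD 1; six tools in total; correlation 0.8 between the tools' test statistics. Multiplicity across taxa is left out.

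**1. Product contrast, one sample per product.**

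SE(paired) = √(2(1−ρ)/n); SE(unpaired) = √(2/n). The effect d is set so that one paired tool has 80% power: d = (1.96 + 0.84) × SE(paired).

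For n = 100 and ρ = 0.5:
- SE(paired) = √(1/100) = 0.100, so d = 0.280.
- SE(unpaired) = √(2/100) = 0.1414.
- Unpaired power = Φ((0.280 − 1.96 × 0.1414)/0.100) = Φ(0.03) = 51%.
- Unpaired type I error = 2(1 − Φ(1.96/√0.5)) = 0.6%.

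| ρ | Unpaired power | Unpaired type I error |
|---|---|---|
| 0.3 | 68% | 1.9% |
| 0.5 | 51% | 0.6% |
| 0.7 | 22% | 0.03% |

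The sample size cancels from these comparisons because d is scaled to the paired standard error, so the planned allowance ("we take into account 5-10% dropout") does not alter them. An unpaired tool is conservative here. The possible harm is lost power, not false findings.

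**2. What a vote does to the product contrast.** Simulation with 200,000 runs, n = 100, ρ = 0.5, d = 0.280:

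| Voting rule | Power | Type I error |
|---|---|---|
| One paired tool | 80% | 5.0% |
| 2 of 3 paired | 82% | 3.7% |
| 3 of 3 paired | 69% | 1.4% |
| 2 of 6 mixed | 83% | 3.9% |
| 4 of 6 mixed | 62% | 0.7% |
| 6 of 6 mixed | 36% | 0.1% |

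If any two tools suffice, admitting three unpaired tools changes power by 83 − 82 = 1 point and type I error by 3.9 − 3.7 = 0.2 points. The loss appears only when the threshold cannot be met by the paired tools alone.

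**3. Pill versus natural cycle, samples pooled as if independent.** With m samples per woman the design effect is DE = 1 + (m − 1)ρ, and the actual alpha is 2(1 − Φ(1.96/√DE)).

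For ρ = 0.5:
- m = 3: DE = 2, alpha 17%; two tools correlated 0.8 agree falsely in 9%.
- m = 5: DE = 3, alpha 26%; false agreement 15%.
- m = 15: DE = 8, alpha 49%; false agreement 33%.

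These error rates would be serious. They apply only to a between-group taxon test on pooled repeats in which tools blind to the participant are enough for agreement.

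**4. Does the text describe the harmful set-ups?**
- It does not say that tools without random effects vote in the paired comparisons.
- It does not set a threshold that would require them.
- It does not describe a pooled pill-versus-natural taxon test. The analysis paragraph opens with the influence of the menstrual products.
- A tool without random effects need not ignore the participant. It can block on the woman as a fixed effect or work on within-woman differences; the ordinary paired t-test has no random-effect term.

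**The case for a change.** The best argument for a change is that the protocol fixes a significance rule, rests its sample size on pairing, and never ties the two together. A literal reader could let any tools vote. A required unpaired tool could then remove much of the power: with an assumed shift of 0.3 SD, 100 women and ρ = 0.5, power is about 84% for the paired test and about 58% if an unpaired test must also agree. Contraceptive group is called a condition in the sample-size paragraph, and the decision rule speaks of taxa by condition, so a between-group test is plausible. One sentence restricting the vote would cost nothing.

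Part of this stands. The wording excludes neither failure, and the arithmetic is right for the scenarios it assumes. What does not stand is the step from a possible reading to a flawed rule. The two harms belong to different contrasts and need different voting rules, and a low threshold avoids the loss of power in the product contrast. The suggested replacement (two of three, a set false-discovery level, same sign) is one reasonable choice among several and cannot be derived from the protocol.

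**Conclusion.** The concern does not call for a change. Read beside the commitment to paired analyses, the sentence on three tools most naturally says that enough tools exist to reach a consensus within the paired design, which is close to the remedy the concern would ask for. The tool list, the agreement threshold and the tools that count in each contrast are not written down, but a protocol commonly leaves these to a statistical analysis plan, and that plan is not at hand. Analysts who already plan paired and mixed-effects analyses can be expected to fill the gap sensibly.

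The size depends wholly on unstated choices. Under the assumed correlation of 0.5 and six tools, power for a product effect ranges from 83% (any two agree) to 36% (all must agree), and type I error stays at or below 3.9% under the mixed votes. False agreement of 9% to 33% for contraceptive group arises only under a pooled analysis that the protocol does not describe. Correlations, effect size, tool count and correlation between tools are all assumptions, so these figures show what could happen under other rules and do not demonstrate an error in this one.
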